### 14.3. Analysis Populations

#### **Safety Population:**

All subjects that complete any study procedures after signing the Informed Consent form (subjects will be wearing their habitual contact lenses in this study). At least one observation should be recorded.

#### **Per-Protocol Population:**

All subjects who have successfully completed all visits and did not substantially deviate from the protocol as determined by the trial cohort review committee prior to database hard lock (Per-Protocol Population). Justification of excluding subjects with protocol deviations in the per-protocol population set will be documented in a memo to file.

#### **Intent-to-Treat (ITT) Population:**

All randomized subjects regardless of actual treatment and subsequent withdrawal from study or deviation from protocol. At least one observation should be recorded.

### 14.4. Level of Statistical Significance

All planned analysis for this study will be conducted with an overall type I error rate of 5%.

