## 2.3. Hypotheses

### Primary Hypotheses

1. Post-treatment subjective scores of comfort (VAS scale) for anesthetized eyes are superior to eyes that received the placebo for at least one of the ocular regions (upper lid margin, lower lid margin, or cornea).
2. Comfort change from pre-treatment for anesthetized eyes is superior to eyes that received the placebo for at least one of the ocular regions (upper lid margin, lower lid margin, or cornea).
3. Post-treatment subjective scores of comfort (VAS scale) for anesthetized eyes are equivalent to 5-minute post lens application levels in the morning for at least one of the ocular regions (upper lid margin, lower lid margin, or cornea). An equivalence margin of 10 points will be used.

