## **5. TEST ARTICLE ALLOCATION AND MASKING**

### **5.1. Test Article Allocation**

An ocular surface region (upper lid margin, lower lid margin or cornea) will be randomly allocated to each visit and a treatment (anesthesia or placebo) will be randomly allocated to each eye using a randomization scheme supplied by the study biostatistician. A single ocular region will be investigated at each visit and a single treatment will be applied to each eye at each visit. The clinical site will follow the randomization scheme provided and will complete enrollment according to the randomization list and will not pre-select or assign subjects. The assignment of the subjects must be performed at Visit 1. The following must have occurred prior to randomization:

- Informed consent has been obtained
- Subject meets all the inclusion / exclusion criteria
- Subject history and baseline information has been collected

The randomization scheme will be generated using the PROC PLAN procedure from the SAS Software Version 9.4 or higher (SAS Institute, Cary, NC).

The regions (upper lid margin, lower lid margin, or cornea) will be treated in a bilateral and random fashion using a Williams design with 3 regions and 3 periods. Each subject will be randomly assigned to one of six unique sequences (U/L/C, L/C/U, C/U/L, C/L/U, U/C/L, L/U/C). For each region within a sequence, the two treatments will be randomly assigned to the left and right eye (anesthesia left eye/placebo right eye or placebo left eye/anesthesia left eye).

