### 14.5. Primary Analysis

#### VAS Comfort

VAS Comfort score at 5 and 10 minutes post treatment will be analyzed separately using a linear mixed model. The model will include the following experimental design factors: treatment, sequence of treatment, region, sequence of region, period, time event, and first-order carryover as fixed effects. Baseline characteristics such as age and gender may be included as covariates when appropriate. The covariance between residual errors for the same subject across periods will be modeled using one of the following covariance structures: Compound Symmetry (CS) or Unstructured (UN). The covariance structure that returns the lowest Akaike Information Criteria Corrected (AICC) will be selected as the structure that best fits the data. The Kenward and Roger method will be used for the calculation of denominator degrees of freedom.

The null and alternative hypothesis for superiority of anesthetized eyes compared to eyes that received the placebo with respect to VAS comfort at post treatment, where  $\mu_A - \mu_P$  is the difference in VAS comfort between anesthesia and placebo treatments, is as follows:

$$\begin{aligned}H_0: \mu_A - \mu_P &\leq 0 \\H_A: \mu_A - \mu_P &> 0\end{aligned}$$

The hypothesis will be tested via corresponding two-sided 95% confidence interval for least-squares mean difference (anesthesia minus placebo) of VAS comfort. Superiority will be concluded if the lower limit is greater than 0 for at least one of the three ocular regions (upper lid margin, lower lid margin, or cornea).

The null and alternative hypothesis for equivalence of VAS comfort scores at post-treatment and 5-minutes post-application, where  $\mu_1 - \mu_2$  is the difference in VAS comfort score between post-treatment and 5-minutes post-application, is as follows:

$$\begin{aligned}H_0: |\mu_1 - \mu_2| &\geq 10 \\H_A: |\mu_1 - \mu_2| &< 10\end{aligned}$$

The hypothesis will be tested via corresponding two-sided 95% confidence interval for least-squares mean difference (post treatment minus post application) in VAS comfort score. Equivalence will be concluded if the upper limit is less than 10 and the lower limit is greater than  $-10$ .

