### VAS Comfort (Change)

VAS Comfort score change from pre-treatment to 5 and 10 minute post-treatment values will be analyzed separately using a linear mixed model. The model will include the following experimental design factors: treatment, sequence of treatment, region, sequence of region, period, and first-order carryover as fixed effects; subject as a random effect. Baseline characteristics such as age and gender may be included as covariates when appropriate. The covariance between residual errors for the same subject across periods will be modeled using one of the following covariance structures: Compound Symmetry (CS) or Unstructured (UN). The covariance structure that returns the lowest Akaike Information Criteria Corrected (AICC) will be selected as the structure that best fits the data. The Kenward and Roger method will be used for the calculation of denominator degrees of freedom.

The null and alternative hypothesis for superiority of anesthetized eyes compared to eyes that received the placebo with respect to VAS comfort change from pre-treatment, where  $\Delta_A - \Delta_P$  is the difference in VAS comfort change from pre-treatment between anesthesia and placebo treatments, is as follows:

$$\begin{aligned}H_0: \Delta_A - \Delta_P &\leq 0 \\H_A: \Delta_A - \Delta_P &> 0\end{aligned}$$

The hypothesis will be tested via corresponding two-sided 95% confidence interval for least-squares mean difference (anesthesia minus placebo) of VAS comfort change from pre-treatment. Superiority will be concluded if the lower limit is greater than 0 for at least one of the three ocular regions (upper lid margin, lower lid margin, or cornea).

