#### 14.6. Secondary Analysis

##### VAS Comfort

The null and alternative hypothesis for superiority of eyes with the cornea anesthetized compared to with upper or lower lid margin anesthetized with respect to VAS comfort at post treatment, where  $\mu_C - \mu_L$  is the difference in VAS comfort between cornea and either lower or upper lid margins, is as follows:

$$\begin{aligned}H_0: \mu_C - \mu_L &\leq 0 \\H_A: \mu_C - \mu_L &> 0\end{aligned}$$

The hypothesis will be tested via corresponding two-sided 95% confidence interval for least-squares mean difference (cornea minus upper or lower lid margin) of VAS comfort. Superiority will be concluded if the lower limit is greater than 0 for at least one of the two differences (cornea minus upper lid margin or cornea minus lower lid margin).

The null and alternative hypothesis for equivalence of VAS comfort scores at lens removal and prior to lens application, where  $\mu_1 - \mu_2$  is the difference in VAS comfort score between lens removal and prior to lens application, is as follows:

$$\begin{aligned}H_0: |\mu_1 - \mu_2| &\geq 10 \\H_A: |\mu_1 - \mu_2| &< 10\end{aligned}$$

The hypothesis will be tested via corresponding two-sided 95% confidence interval for least-squares mean difference (lens removal minus prior to lens application) in VAS comfort score. Equivalence will be concluded if the upper limit is less than  $\delta$  and the lower limit is greater than  $-10$ .

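### Section 14.4 promises an overall 5% type I error, but the unadjusted any-one-of-three-regions rule in 14.5 gives up to 7.3% false superiority for a single time point and scale

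*Combined protocol and SAP*

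**What the plan says.** Section 14.4 is one sentence: "All planned analysis for this study will be conducted with an overall type I error rate of 5" per cent. It covers all planned analysis and does not state sidedness.

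Section 14.5, VAS Comfort, tests anesthesia minus placebo by a two-sided 95% confidence interval and decides as follows: "Superiority will be concluded if the lower limit is greater than 0 for at least one of the three ocular regions". The VAS Comfort (Change) part repeats the rule on change from pre-treatment. Both are run twice: "VAS Comfort score at 5 and 10 minutes post treatment will be analyzed separately using a linear mixed model", and likewise "VAS Comfort score change from pre-treatment to 5 and 10 minute post-treatment values will be analyzed separately using a linear mixed model".

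The same any-one structure appears elsewhere:

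- Primary hypothesis 3 (section 2.3): post-treatment scores "are equivalent to 5-minute post lens application levels in the morning for at least one of the ocular regions". The equivalence rule in 14.5 does not itself say how the regions combine.
- Both secondary superiority rules (section 14.6): "Superiority will be concluded if the lower limit is greater than 0 for at least one of the two differences".

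The score model lists "treatment, sequence of treatment, region, sequence of region, period, time event, and first-order carryover as fixed effects". The change model lists the same design factors without time event, plus a random subject effect. Neither lists a treatment-by-region term.

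Sections 2.3 and 14.1 to 14.10 contain no multiplicity adjustment or hierarchy, and do not say which time point or scale decides. Section 14.1 calls the study a feasibility study and 14.2 calls it a pilot.

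**The concern.** A win in any one of three regions, each tested at an unadjusted level, has a higher chance of a false win than a single test. An overall 5% cannot simply be asserted alongside that rule. It has to follow from the intervals, the number of comparisons and the way results are combined.

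At stake is how a positive result is read. A report could present superiority in one region, at one time, on one scale, and cite 14.4 for an overall 5% error that the decision rule does not provide. Because the deciding time point and scale are left open, that choice could also be made after the data are seen.

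**Working it through.** **Inputs.** From section 14.2: 15 completers, SD 15 or 20, intraclass correlation (ICC) 0.4 to 0.8, equivalence margin ±10. From 14.5: two-sided 95% intervals, three regions, two times, two scales. Correlations between regions, between times, and between pre- and post-treatment scores are not given; those below are assumptions. A paired t-test with 14 degrees of freedom stands in for the mixed model.

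**Step 1: the plan's own figure.** With SD of the difference = SD × √(2(1 − ICC)), the cell for 7.5 points, SD 15, ICC 0.8 has SD of the difference 15 × √0.4 = 9.49 and noncentrality 7.5 × √15 / 9.49 = 3.06.

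- One-sided 0.05: power 0.897, as printed in Table 3.
- Two-sided 0.05, as listed in 14.2 and used in 14.5: power 0.812.

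All 18 cells of Table 3 match one-sided 0.05, and Table 4 matches 0.05 per side. So 14.2 contradicts itself on sidedness and cannot supply the benchmark. The benchmark has to be the 5% in 14.4.

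**Step 2: one time, one scale, three regional contrasts.** A lower 95% limit above 0 has a false-positive rate of 0.025 per region. If regions are independent, 1 − 0.975³ = 0.0731.

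Independence is reasonable for these between-eye contrasts because of section 5.1: "For each region within a sequence, the two treatments will be randomly assigned to the left and right eye". A stable right–left difference within a subject therefore does not carry over systematically from region to region. If the contrasts were still positively correlated:

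| Region correlation (assumed) | False superiority |
|---|---|
| 0 | 7.3% |
| 0.2 | about 7.1% |
| 0.5 | about 6.3% |
| 0.8 | about 5.0% |

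The rate comes down to 5% only at a correlation of about 0.8.

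**Step 3: two time points.** With independent regions, an assumed 5/10-minute correlation of 0.7 to 0.95 and an assumed pre/post correlation of 0.3 to 0.7:

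| How the times combine (not stated) | Score | Change |
|---|---|---|
| A win at either time counts | 9.3–12.3% | 9.3–13.1% |
| The same region must win at both times | 2.2–5.1% | 1.2–5.5% |

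**Step 4: primary hypothesis 3.** Suppose all three regions truly differ by 10 points and any one suffices. At SD 15 and ICC 0.8, false equivalence is about 7.3%, 7.1%, 6.3% and 5.1% at region correlations 0, 0.2, 0.5 and 0.8. With independent regions and the other SD/ICC pairs tried, it runs from 6.2% (SD 15, ICC 0.4) to 7.3%. Eye randomization does not support independence here, because the comparison is with the subject's own morning score in the anesthetized eye.

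**Step 5: secondary any-of-two rules.** With the cornea shared between the two differences and independent regions, the rate is about 4.6% for one time and one scale. That is within a literal 5%.

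**Step 6: the model as listed.** Without a treatment-by-region term, the three regional differences are one contrast, tested at 2.5%. The four time-by-scale tests would then give 5.7–8.3% if any win counts.

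**The case against.** The strongest reply is that this is a pilot. Section 14.2 says the sample size was not based on a power calculation, and 14.1 allows further exploratory analysis. That stands as a reason not to demand formal control. It does not make 14.4 true, because that sentence is unconditional.

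A second reply is that the listed models give one common treatment difference, so there is nothing to multiply. Taken literally that is correct for one time and one scale. But it contradicts the plan's own rule, which speaks of three regions, and it leaves four separate tests. The 7.3% therefore describes the analysis the rule implies, not the model as listed.

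A third reply is that requiring a win at both times would bring the rate to about 5% or lower. It could, but the plan does not say so.

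Two stronger readings are tempting. One is that 7.3% is about three times a 2.5% rate set by 14.2. The tables in 14.2 were computed at one-sided 0.05, so that section does not fix 2.5%. The figure applies only if the 5% in 14.4 is meant as two-sided. The other is that the secondary rules break the promise too. At about 4.6% for one time and scale, they exceed it only on that same two-sided reading.

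**Conclusion.** The overall 5% in 14.4 is not delivered by the superiority rule in 14.5. For one time and one scale the rate is 7.3% with independent regions and about 5.0% at a region correlation of 0.8. This rests on region-specific contrasts and on a paired t-test in place of the mixed model. Primary hypothesis 3 has the same structure, at up to about 7.3% under independence and about 5% at correlation 0.8 (SD 15, ICC 0.8).

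A reader might infer one error rate for the whole plan, such as 13%. The documents do not support that. They give neither the correlations nor the rule for combining times and scales, and different readings fall on either side of 5%. The finding is an explicit commitment that the decision rules do not back. It should be corrected, but its weight in a pilot is modest.

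**What to change.** **Main change.** Replace the sentence in 14.4 with: *Each comparison uses a two-sided 95% confidence interval; the overall type I error rate across regions, time points, outcomes and hypotheses is not controlled.* Add the treatment-by-region term to both models in 14.5, since the per-region rule needs it. These are wording changes. The 95% intervals stay as they are, so the regional comparisons lose no power.

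**Option, with a real trade-off.** If the sponsor wants to keep an overall claim, limit it to one named outcome at one named time point over three regions, and label everything else supportive, including primary hypothesis 3 and all secondary hypotheses. Single-region power below is for n = 15, SD 15, ICC 0.8:

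| Interval per region | False superiority (independent regions) | Power at 7.5 points | Power at 10 points |
|---|---|---|---|
| 95% (current) | 7.3% | 0.812 | 0.966 |
| 96.67%, holding 5% | 1 − (1 − 0.05/3)³ = 4.9% | 0.752 | 0.946 |
| 98.33%, if 5% is two-sided | 1 − (1 − 0.025/3)³ = 2.5% | 0.638 | 0.896 |

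Table 3 prints 0.897 where this table starts from 0.812, because Table 3 was computed at one-sided 0.05 and 14.5 uses two-sided 95% intervals.

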### 14.5. Primary Analysis

#### VAS Comfort

VAS Comfort score at 5 and 10 minutes post treatment will be analyzed separately using a linear mixed model. The model will include the following experimental design factors: treatment, sequence of treatment, region, sequence of region, period, time event, and first-order carryover as fixed effects. Baseline characteristics such as age and gender may be included as covariates when appropriate. The covariance between residual errors for the same subject across periods will be modeled using one of the following covariance structures: Compound Symmetry (CS) or Unstructured (UN). The covariance structure that returns the lowest Akaike Information Criteria Corrected (AICC) will be selected as the structure that best fits the data. The Kenward and Roger method will be used for the calculation of denominator degrees of freedom.

The null and alternative hypothesis for superiority of anesthetized eyes compared to eyes that received the placebo with respect to VAS comfort at post treatment, where  $\mu_A - \mu_P$  is the difference in VAS comfort between anesthesia and placebo treatments, is as follows:

$$\begin{aligned}H_0: \mu_A - \mu_P &\leq 0 \\H_A: \mu_A - \mu_P &> 0\end{aligned}$$

The hypothesis will be tested via corresponding two-sided 95% confidence interval for least-squares mean difference (anesthesia minus placebo) of VAS comfort. Superiority will be concluded if the lower limit is greater than 0 for at least one of the three ocular regions (upper lid margin, lower lid margin, or cornea).

The null and alternative hypothesis for equivalence of VAS comfort scores at post-treatment and 5-minutes post-application, where  $\mu_1 - \mu_2$  is the difference in VAS comfort score between post-treatment and 5-minutes post-application, is as follows:

$$\begin{aligned}H_0: |\mu_1 - \mu_2| &\geq 10 \\H_A: |\mu_1 - \mu_2| &< 10\end{aligned}$$

The hypothesis will be tested via corresponding two-sided 95% confidence interval for least-squares mean difference (post treatment minus post application) in VAS comfort score. Equivalence will be concluded if the upper limit is less than 10 and the lower limit is greater than  $-10$ .

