## 2.2. Endpoints

### Primary Endpoint(s)

The primary endpoint is the subjective scores of comfort (VAS scale) collected at various time points:

- Immediately prior to lens application
- 5 minutes after lens application
- 14 hours after lens application (i.e. pre-treatment)
- Immediately after lens removal prior to treatment application, only for the cornea.
- 5 minutes post-treatment
- 10 minutes post-treatment

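### The plan tests the primary hypotheses at both 5 and 10 minutes after treatment, each at an unadjusted 95% level, and never says which time decides

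*Combined protocol and SAP*

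**What the plan says.** Section 2.2 does not fix a single response: "The primary endpoint is the subjective scores of comfort (VAS scale) collected at various time points". It lists six times, two of them after treatment (5 and 10 minutes).

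The primary hypotheses in Section 2.3 give no post-treatment minute:
- Hypothesis 1: "Post-treatment subjective scores of comfort (VAS scale) for anesthetized eyes are superior to eyes that received the placebo".
- Hypothesis 2: "Comfort change from pre-treatment for anesthetized eyes is superior to eyes that received the placebo".
- Hypothesis 3: post-treatment scores "for anesthetized eyes are equivalent to 5-minute post lens application levels in the morning". The five minutes here belong to the morning reference score, not to the post-treatment score.

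Section 14.5 then runs each analysis twice. For the score: "VAS Comfort score at 5 and 10 minutes post treatment will be analyzed separately using a linear mixed model". For the change: "VAS Comfort score change from pre-treatment to 5 and 10 minute post-treatment values will be analyzed separately using a linear mixed model". The superiority rule for the score reads "The hypothesis will be tested via corresponding two-sided 95% confidence interval for least-squares mean difference (anesthesia minus placebo) of VAS comfort", and success needs a lower limit above 0 in at least one of three regions. The change score has a parallel rule. The equivalence rule compares both limits with ±10. None of these rules says whether 5 minutes, 10 minutes, either or both must succeed.

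Section 14.4 states: "All planned analysis for this study will be conducted with an overall type I error rate of 5" per cent. No hierarchy, split or adjustment is given there or elsewhere.

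**The concern.** Followed exactly, the plan gives two answers to each primary hypothesis. If they agree, nothing is lost. If they differ, the plan does not say whether the hypothesis is supported, and the favourable time can be chosen after the results are known. Reading success at either time as success also gives every region a second chance at the same unadjusted level. That adds to the error already created by accepting any one of three regions. The two issues are separate: a full correction for regions would still leave the choice of time open.

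**Working it through.** **Inputs from Section 14.2:** 15 completers; true difference 7.5 points; SD 15 or 20; intraclass correlation (ICC) 0.8. **From Section 14.5:** two-sided 95% interval, so 2.5% error in the favourable direction; any one of three regions suffices. **Assumed:** correlation ρ between the 5- and 10-minute anesthesia-minus-placebo differences of 0.5, 0.7 and 0.9; regions either independent or correlated 0.5. Simple paired t-tests stand in for the mixed model, and one hypothesis is taken at a time.

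**1. The plan's own figure.** SD of a paired difference = SD × √(2(1 − ICC)) = 15 × √0.4 = 9.49. Noncentrality = 7.5 / 9.49 × √15 = 3.06, with 14 degrees of freedom. Table 3 gives 0.897. This reproduces with a one-sided 5% test. With the 95% interval that Section 14.5 actually uses (cut-off t = 2.145) the power is 0.812. That mismatch is a separate matter, but it makes 0.812 the right baseline here.

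**2. Error when success at either time counts.** Correlated paired t-tests were simulated with n = 15 and no true effect. For three independent regions the error is 1 − (1 − e)³, where e is the one-region error. With one deciding time this is 1 − 0.975³ = 7.3%.

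| ρ | one region, one time | one region, either time (e) | any of 3 independent regions, either time |
|---|---|---|---|
| 0.5 | 2.5% | 4.5% | 1 − 0.955³ = 12.9% |
| 0.7 | 2.5% | 4.2% | 1 − 0.958³ = 12.1% |
| 0.9 | 2.5% | 3.6% | 1 − 0.964³ = 10.4% |

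Simulation runs differ by about 0.1 percentage point in e. The ceiling, at ρ = 0, is 1 − 0.975² = 4.9% for one region. With regions correlated 0.5, the any-region error goes from about 6.4% at one time to about 11% (ρ = 0.5) down to about 9% (ρ = 0.9). Equivalence behaves alike: with the true difference at the margin, the one-region error is 2.5% at one time and 3.6–4.5% at either.

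**3. How often the two times disagree.** Raw score, one region, true effect 7.5 points at both times, ICC 0.8:

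| ρ | SD 15 | SD 20 |
|---|---|---|
| 0.5 | 22% | 34% |
| 0.7 | 17% | 26% |
| 0.9 | 10% | 15% |

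**4. Change score.** Let r be the pre-post correlation of the between-eye difference, taken as equal at both times. The two changes then correlate (ρ − 2r + 1)/(2 − 2r), and the SD is multiplied by √(2 − 2r). For SD 15, ICC 0.8 and ρ = 0.5, disagreement is 26%, 22% and 8% at r = 0.3, 0.5 and 0.7. For ρ = 0.7 it is 20%, 17% and 7%. Single-time power is 0.67, 0.81 and 0.96 at the same three values of r. The raw-score figures therefore do not carry over to hypothesis 2.

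**5. Averaging as a remedy.** For superiority, the mean of the two times keeps the error at 2.5% and raises power from 0.81 to 0.91, 0.87 and 0.83 (ρ = 0.5, 0.7, 0.9). For equivalence, suppose the true difference is −12 at 5 minutes and 0 at 10 minutes. The mean is −6, inside the margin. The mean declares equivalence in about 42%, 38% and 35% of trials; the 5-minute test alone does so in 0.3%.

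**The case against.** - **Time-point choice does not breach 5% by itself.** A reader might infer that taking either time breaks the overall rate in Section 14.4. The figures do not support this: for one region the error is at most 4.9%, and Section 14.4 does not state sidedness. The rate passes 5% only together with the any-region rule, which already gives about 7% alone. This objection stands, and the claim is limited accordingly.
- **Section 14.4 already controls the error.** It states an aim but provides no means of reaching it, while Section 14.5 uses unadjusted intervals throughout.
- **Time is in the model.** The score model lists a time-event factor, but the change model does not, the two times are analyzed separately, and no decision rule uses the factor to combine them.
- **Differing verdicts are not contradictory evidence.** Correct: one interval excludes 0 and the other does not. Both analyses are pre-specified and can be reported by time. What is missing is the rule turning them into one conclusion.
- **This is a small pilot.** The synopsis calls it phase 0, and Sections 14.1 and 14.2 call it a feasibility and pilot study. That lowers the stakes. The plan still sets formal hypotheses, a margin and an error rate, and these need a defined response.
- **Both times lie within the period of numbness, so they measure one effect.** A reader might conclude that averaging is safe everywhere. The 15-minute-to-one-hour figure concerns anesthesia, whereas the endpoint is comfort. Eyelid eversion and brushing, or lens removal and reapplication, precede the 5-minute score, so early irritation is plausible.

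**Conclusion.** The concern holds in a limited form. No section names the post-treatment time that decides primary hypotheses 1 to 3, and 15 completers make differing results realistic: about 10–22% on the raw score at 7.5 points, SD 15 and ICC 0.8. On the change scale the frequency also depends on the pre-post correlation. Either-time success raises the one-region error above the nominal 2.5% but keeps it under 5%. With the any-region rule it adds roughly 3 to 6 percentage points to an error already near 7%. These sizes rest on an assumed 5-versus-10-minute correlation, assumed region correlations and paired t-tests in place of the mixed model. The absence of a deciding rule rests on none of those assumptions.

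**What to change.** In Sections 2.2 and 14.5, name one post-treatment time as deciding hypotheses 1 to 3, and state that the other is supportive and carries no separate claim. Fix the choice before data are seen. This needs a few words and no new data. It returns the favourable-direction error to 2.5% per region, with power 0.812 in the case worked above. It does not cure the any-of-three-regions rule, which needs its own correction.

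The mean of the two times may be used instead for hypotheses 1 and 2 (for hypothesis 2, the mean minus the pre-treatment score). It should not be used for hypothesis 3, where it can hide a difference outside the margin at one time. Keeping both times as deciding costs power: 97.5% intervals give 0.706 per time, and requiring success at both gives about 0.70–0.76.

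The cost of naming one time is that an effect seen only at the other would not support a primary claim.
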